8.1.6 Management of study participants

Subjects found to harbor gametocytes will be admitted for a period of approximately 24 hours to an observation ward at the Kombewa CRC or the Kombewa sub-county hospital located across the street from the CRC while awaiting their second feed as described above. While in the ward, they will be encouraged to dress in clothing that covers most of the skin so as to minimize contact with mosquitoes. In order to allow for the successful execution of the mosquito feeding assays, all gametocytic participants will be offered antimalarial treatment only after completion of all feeding assays. A full course of artemether/lumefantrine 480/80mg (Coartem®) along with a single low dose of primaquine (15 mg primaquine base) will be administered as per the package insert – primaquine and the first dose of Coartem® will be witnessed by study staff. Primaquine will not be given to pregnant or breastfeeding women. Given that PCR testing tends to detect parasite levels much lower than the detection limit of standard clinical tests for malaria (RDT and microscopy), standard clinical testing will not be performed prior to administration of antimalarial treatment to clear parasitemia. Administration of primaquine to malaria patients is not part of standard care in Kenya. Primaquine, however, is specifically effective against gametocytes and therefore serves the purpose of ensuring clearance of circulating gametocytes in the participant. The administration of antimalarials to asymptomatic individuals is currently not part of standard of care in Kenya.

Gametocytic participants who show signs of malaria while under observation will be managed in accordance to the Kenya MoH National Guidelines for the Diagnosis, Treatment and Prevention of Malaria. Such participants will not participate in further feeding assays and will be replaced until the desired sample size is achieved.

Study participants who withdraw consent while under observation and are still asymptomatic will be offered antimalarial treatment to clear parasitemia as described above prior to leaving the observation

ward. If they are symptomatic, they will be offered the choice to be managed by the study clinical team in accordance to the Kenya MoH National Guidelines for the Diagnosis, Treatment and Prevention of Malaria, or be referred to the Kenya Ministry of Health clinician for further management.

8.1.7 Standard of care study procedures

According to the Kenya MoH National Guidelines for the Diagnosis, Treatment and Prevention of Malaria, patients presenting with signs and symptoms of malaria will get tested for malaria (either by rapid diagnostic test or microscopy) and treatment offered immediately upon receiving the test results. Artemisinin based combination therapy (ACT) (for example artemether lumefantrine) would be typically prescribed for uncomplicated malaria, and intravenous artesunate would be prescribed for severe malaria. In certain cases, presumptive treatment of malaria is allowed. Additionally, drugs for alleviating symptoms, such as antipyretics for fever, are also typically prescribed.

For this study, asymptomatic participants will be recruited and tested for presence of gametocytes. They will receive malaria treatment as described in section 8.1.5.

8.1.8 Clinical laboratory procedures

A urine pregnancy test using a commercially available human chorionic gonadotropin (hCG) based test will be done in all females of child-bearing potential at screening and repeated no more than 24 hours prior to administration of primaquine, with all pregnant women being excluded. Clinical laboratory tests that are needed to guide subject treatment for emergent clinical malaria will be requested by the attending clinician in accordance to the Kenya MoH guidelines.

8.1.9 Other assays or procedures

8.1.9.1 Malaria blood film microscopy

Two glass microscope slides will be prepared by the project laboratory technician from the whole blood sample obtained from each volunteer at the screening visit, and prior to mosquito feeding assays in accordance to site SOPs, each with one thick and one thin blood film. The slides will be batched and read at a later date and thus will not influence the decision of whether to perform feeding assays or not. The primary purpose of collecting the slides is to classify gametocyte carriage as microscopic or sub-microscopic during data analysis. The slides will also be used as a quality control tool for the molecular assays described in section 8.1.8.2. An additional slide may be collected in an acutely ill subject to guide management – this slide will be read immediately, and the results shared with the study clinician.

A minimum of 200 microscopic fields will be examined to determine presence or absence of sexual (gametocytes) and asexual malaria parasites on the thick smear. If asexual parasites are found on the thick smear, the thin smear will be evaluated for *Plasmodium* speciation. If gametocytes are present, the male to female ratio will be determined. The findings of two expert microscopists will be considered. A third expert microscopist will be used to resolve any discrepant results.

8.1.9.2 *Plasmodium* detection molecular assays

Gametocyte RT-PCR will be performed overnight or on the day following blood collection on all eligible subjects that consent for the study and results will be used to guide mosquito feeding assays to be performed on gametocytic individuals. Total nucleic acids (DNA/RNA) will be isolated from blood

samples and then PCR amplification of the *Plasmodium* 18s small subunit ribosomal RNA (rRNA) metabolic gene will be performed to detect *P. falciparum*, *P. ovale* and *P. malariae* parasites. For gametocyte RT-PCR, RNA will be reverse-transcribed and the resulting cDNA will be used to amplify gametocyte-specific gene targets. Among the markers that shall be used are *pfs16*, *pfs25* and *pfGMET*. For quantification, positive control standards with known densities will be included and used to generate a standard curve. Parasite density of unknown samples will then be extrapolated from the standard curve. These assays will specifically help quantify both parasitemia and gametocytemia below the current level of detection of microscopy. Participants who are found to have gametocytes by the RT-PCR will be invited to participate in mosquito feeding assays.

8.1.9.3 Oocyst and sporozoite detection and quantification

Approximately half of fed mosquitoes will be maintained for 9-10 days post feeding for detection and quantification of oocysts in the midgut. Briefly, midguts will be dissected from mosquitoes, stained with 1% mercurochrome and examined by microscopy. Oocyst numbers in each midgut will be recorded.

The remainder of fed mosquitoes will be maintained for 14-15 days post-feeding for detection and quantification of sporozoites. Briefly, salivary glands will be dissected from live mosquitoes submerged in phosphate-buffered saline (PBS) in order to visualize motile sporozoites by microscopy. Sporozoite prevalence will be recorded.

The dissected mosquitoes will be processed for detection and quantification of oocysts and sporozoites by molecular methods. After microscopy, slides containing midguts will be flooded with PBS to allow easy removal of coverslips, and excess mercurochrome will be removed by dragging the midgut gently through a clean PBS droplet. Mosquito carcasses will then be homogenized in glass grinding tubes with 180 μ L of PBS and stored in 180 μ L of DNA Tissue Lysis buffer at -80°C in preparation for PCR analysis.

Nucleic acid extraction will be performed using commercial extraction kits following the manufacturer's instructions. *P. falciparum* parasite detection and quantification will be undertaken using the 18S rRNA gene target. To quantify the number of genomes detected in the mosquito midguts and salivary glands using the 18S qPCR assay, a standard curve generated using synthetic plasmid DNA will be used.

8.1.10 Specimen Preparation, Handling, and Storage

Whole blood collected in EDTA tubes from the field will be sent to the MDR central laboratory located on the KEMRI campus for processing (see section 8.1.3 for details). Specimens will be stored at KEMRI/USAMRD-A facilities. Filter paper and whole blood samples will be stored at -80°C. DNA and RNA extracts will be stored at +4°C if intended for immediate use or -20°C if intended for near future use. The remaining DNA and RNA will be stored appropriately at -80°C and retrieved whenever they need to be analyzed. Serum will be stored at -80°C until required for analyses. At the end of the study, after all analyses have been completed, any remaining samples will be destroyed.

9. ASSESSMENT OF SAFETY

9.1 Adverse Events (AE)

Local solicited AEs, as defined in this protocol, include pruritus and erythema at the site of the mosquito bite, in a study participant following DSFA on days 1 and 2. Unsolicited AEs will be captured in study participants after informed consent is obtained and until the subject completes all study procedures.

9.2 Serious Adverse Event

An AE or suspected adverse reaction is considered "serious" if, in the view of either the investigator or sponsor, it results in any of the following outcomes: death, a life-threatening adverse event, inpatient hospitalization, a persistent or significant incapacity or substantial disruption of the ability to conduct normal life functions, or a congenital anomaly/birth defect. Important medical events that may not result in death, be life-threatening, or require hospitalization may be considered serious when, based upon appropriate medical judgment, they may jeopardize the patient or subject and may require medical or surgical intervention to prevent one of the outcomes listed in this definition.

9.3 Classification of An Adverse Event

For AEs, the following guidelines will be used to describe severity.

- Mild – Events require minimal or no treatment and do not interfere with the participant's daily activities.
- Moderate – Events result in a low level of inconvenience or concern with the therapeutic measures. Moderate events may cause some interference with functioning.
- Severe – Events prevents a participant's usual daily activity.

9.4 Time Period and Frequency of Event Assessment and Follow-up

The investigator will record all reportable events with start dates occurring any time after informed consent is obtained until the last day of study participation. All AEs not meeting the criteria for severe adverse events (SAEs) will be captured on the appropriate case report form.

9.5 Reporting Procedures

9.5.1 Adverse event and Serious Adverse Event reporting

All serious adverse events (SAEs) will be promptly (within 48 hours) reported to the KEMRI SERU and to the WRAIR IRB. Prompt (within 48 hours) reports will be submitted to the KEMRI SERU by email ([contact]; [contact]) and to the WRAIR IRB by [contact], or by email ([contact]), or by [contact]. The Principal Investigator will then submit written reports within 10 working days to the WRAIR IRB at the following address: Walter Reed Army Institute of Research, ATTN: Human Subject Protection Branch (HSPB), [name], [name] 20910.

Any SAEs or other events that meet PATH Research Ethics Committee's (REC) expedited reporting requirements will be promptly (within 24 hours) reported to the PATH Study Representative by email. The PATH Study Representative will then promptly (within 48 hours) submit the report to PATH REC using their online submission and reporting website (www.irbnet.org).

Follow up reports will be submitted as additional information becomes available. A summary of the non-serious adverse events and the SAEs (both related and unrelated) that occurred during the reporting period should also be included in the continuing review report to the KEMRI SERU, and the WRAIR IRB. The WRAIR HSPB will report SAEs to the USAMRMC ORP HRPO as per WRAIR SOP UWZ-C-636.

9.5.2 Unanticipated problems and UPIRTSOs

All non-serious unanticipated problems (events not involving risk to participants or others) will be reported in the continuing review/progress report to the WRAIR IRB and KEMRI SERU.

All serious unanticipated problems involving risk to participants or others should promptly (within 48 hours) reported to the WRAIR IRB and KEMRI SERU. The Principal Investigator will then submit a written report within 10 working days to the WRAIR IRB and KEMRI SERU.

Follow up reports should be submitted as soon as additional information becomes available. A summary of the serious unanticipated problems will also be included in the continuing review/progress report submitted to the WRAIR IRB and KEMRI SERU.

9.5.3 Pregnancies

Each pregnancy must be reported *promptly (within 48 hours of identification)* by email to the WRAIR IRB and KEMRI SERU.

9.5.4 Continuing Review/Progress Reports

The PI or designee will be responsible for submitting the required continuing review/progress reports and supporting documentation, as appropriate, to the WRAIR IRB and KEMRI SERU, allowing sufficient time for review and continuation determination prior the established continuing review/progress report date. A closeout report will be submitted at the end of the study upon completion of all the study activities or 5 years, whichever comes first.

9.5.5 Inspections and audits

Knowledge of any pending compliance inspections/visits by Office for Human Research Protections (OHRP) or other government agency concerning clinical investigation or research, the issuance of Inspection Reports, warning letters or actions taken by any Regulatory Agencies including legal or medical actions and any instances of serious or continuing noncompliance with the regulations or requirements will be reported immediately to the KEMRI SERU ([contact]; [contact]) and WRAIR IRB by [contact], or by email ([contact]), or by [contact]. The WRAIR HSPB will report to USAMRDC ORP HRPO as per SOP UWS-HP-636.

9.5.6 Protocol deviations

Major protocol deviations are a subset of protocol deviations that may significantly impact the completeness, accuracy, and/or reliability of the study data or that may significantly affect a subject's rights, safety, or well-being. The principal investigator will not implement any deviation from or changes to the protocol without the agreement of PATH and prior review from all IRBs except where necessary to eliminate an immediate hazard to trial subjects or when the change involves only logistical or

administrative aspects of the trial. The PI will ensure that deviations from the protocol are documented and reported to PATH.

Major/significant deviations must be reported to the WRAIR IRB and KEMRI SERU within 48 hours of becoming aware of the event. A written report must be submitted within 10 working days of knowledge of the event to the WRAIR IRB and KEMRI SERU.

All deviations, including minor/non-significant deviations, will be reported to the WRAIR HSPB/IRB and KEMRI SERU in a cumulative summary report with each continuing review/progress report and with the study closeout report. These reports will include descriptions of the deviation, any actions taken in response to the deviation and an assessment of the impact of the deviation.

All subject-specific deviations from the protocol (e.g., failure to return for follow-up visits or blood collection within the time indicated in the protocol) are to be documented. The PI or designee will be responsible for identifying and reporting all deviations, which are defined as isolated occurrences involving a procedure that did not follow the study protocol or SSP. Action taken in response to the deviation, and the impact of the deviation will be assessed by the PI or sub investigator and recorded as Major or Minor as per the WRAIR HSPB definitions. Deviations will be reported in the continuing review/progress report to the WRAIR IRB and the closeout report.

Any protocol deviation that adversely affects the safety or rights of a subject or scientific integrity of the study, the deviation will be reported within 48 hours of recognizing the deviation, to the WRAIR IRB and KEMRI SERU with a written report submitted within 10 working days.

10. STATISTICAL CONSIDERATIONS

10.1 Overview and General Design

This is a single center and single group study designed to better understand the relationship between parasite transmission from humans to mosquitoes, within a person, across persons, and by both DSFA and DMFA performed at two consecutive time points.

10.2 Statistical Hypothesis

We are interested in assessing the equivalence of oocyst prevalence measured in the same subject undergoing DSFA at two consecutive 24-hour time periods. If the difference in oocyst prevalence measured on two consecutive days is represented as Δ , the null (H_0) and alternative (H_1) hypotheses of the primary efficacy endpoint analysis are as follows:

$$H_0: \Delta > \Delta_E \text{ or } \Delta < -\Delta_E$$

$$H_1: -\Delta_E < \Delta < \Delta_E$$

Where Δ_E represents a value such that range that would support the use of a “before-after” trial design in a future mAb study.

10.3 Sample Size

This is a clinical investigation study where there is no prior knowledge related to the oocyst prevalence or density on a repeated DSFA or DMFA in a human subject. As such, the sample size chosen for this study was primarily based on logistical and budgetary considerations that would estimate the variability in DSFA. The results of this experimental medicine trial would be to ascertain the feasibility of using a paired “before-after” study design in same individual in a future trial when a TRI is introduced.

[figure not shown]
There are two unknowns and a major constraint in arriving at a meaningful sample size for the current trial challenging. First, there is no prior data in metrics of DSFA in same person at 2 consecutive time points. Secondly, there is a wide range of initial gametocyte densities in persons at baseline screening which may markedly influence the transmission and development of parasites from man-to-mosquito and detection of oocysts in the mosquito midgut 9 days after a blood meal.

Prior data obtained from the same site and same investigators in Kenya indicate that:

Approximately 25% of persons at any one time will have positive *P. falciparum* gametocytes by PCR

Of those that are positive for *P. falciparum* gametocytes and who have undergone DSFA, there will be a distribution of oocyst-positive mosquitoes (defined as positive event) detected 9 days after a mosquito feed as shown below.

Figure 9: Prevalence of infected mosquitos. Unpublished data from previous study

[figure not shown]

It is important to note that in approximately 16% of experiments with PCR-positive gametocytes, there will be no (zero) infected mosquitoes detected.

Greater than 50% of DSF assays have < than 5 infected mosquitoes out of 25 that were found to have oocysts detected in the midgut 9 days after a blood meal.

As the budget for the trial is constrained, we estimate a sample size below that will have 45 consented individuals out of 400 screened with positive *P. falciparum* gametocytes of whom will have an estimated transmissibility on day 1 indicated in the figure below. It is unknown whether the same level of transmissibility occurs on day 2 in the same person which is the subject of the proposed trial. The sample size proposed below provides for a reasonable and logically feasible number of subjects (n=36) that will have two consecutive DSFA performed across a range of positive events.

Figure 10: Study sample size

[figure not shown]

With these limitations in mind a simulation approach was used to understand the power to reject various equivalence null hypotheses ($-\Delta_E, \Delta_E$) assuming either high correlation within subjects for consecutive DSFA or independence between measurements.

Briefly, we assume that the number of positive mosquitos for any DSFA is binomially distributed $x_{it} \sim \text{Bin}(25, p_{it})$ where $p_{it} \sim \text{Beta}(1.5, 6)$. The parameters for the Beta distribution were selected to generate a distribution of positive mosquitos which achieves, approximately, the characteristics listed in points 3 and 4 above (16% with 0 positive mosquitos and 50% less than 5). For a single draw of $x_t = x_{1t}, \dots, x_{36t}$, the distribution of mosquitos looks similar to the data observed above.

[figure not shown]
We considered two scenarios in our simulations. First, we assume that observations within person on consecutive days are independent. That is, $x_{i1} \sim \text{Bin}(25, p_{i1})$ and $x_{i2} \sim \text{Bin}(25, p_{i2})$ where p_{i1} and p_{i2} are independent draws from the Beta distribution. Second, we assume the underlying transmission probability within a person is constant for the two consecutive feeds and $x_{i1} \sim \text{Bin}(25, p_i)$ and $x_{i2} \sim \text{Bin}(25, p_i)$ where $p_i = p_{i1} = p_{i2}$. A simulated example for these two scenarios is shown in the figure below.

Figure 11. Simulating scenarios with independent daily transmission probabilities within subjects (left) or constant transmission probabilities over 24 hours within subjects (right).

[figure not shown]
We simulated this experiment based on both of the scenarios and then used a paired t-test to test for equivalence in oocyst prevalence at various equivalence intervals ($-\Delta_E, \Delta_E$). We find that with the current sample size of 36 subjects and 25 mosquitos per feeding assay, we will have 90% power to reject the null hypothesis that the difference of oocyst prevalence between consecutive feeding assays is greater than $+\/-7\%$ for correlated data (scenario 2). However, the same equivalence interval ($\Delta_E=0.07$) has only 4% power assuming independent data (scenario 1). Power for the equivalence test over a range of equivalence intervals and both scenarios are shown in the figure below.

Figure 12. Power calculation for equivalence test

The data collected in this study will help inform the design of follow on studies by informing parameter values of interest, such as the correlation between subsequent feeds, to assess the power to measure monoclonal antibody or drug efficacy with before-after or two-group designs under various sample sizes and efficacy assumptions. For example, in the figures below independent data has an average correlation of 0.0 and is compared with a t-test and correlated data has an average correlation of 0.5 and is tested with a paired t-test. Using the parameters of the simulated data above we can investigate the impact of sample size and design on the power to detect varying levels of efficacy. The real data from this study will help inform this parameter space.

Figure 13. Estimated power calculation for follow-on Phase 2b trial design

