8.1.4 Enrolment of gametocytemic participants

Participants who are found to harbor gametocytes as per the PCR test (with a cT value of less than 31) will be enrolled to participate in the mosquito feeding assays. The MDR expects to turn around the results of the PCR tests within approximately 48 hours of sample collection. The results of the tests will be communicated to the study team in Kombewa, who will then contact the participants. For participants who do not have gametocytes detected, they will be informed of the results and the study team will explain to them that their participation has ended. Participants who are gametocytemic will be invited to participate in the mosquito feeding assays. Participants who are found to have very low density gametocytemia (PCR cT value of 31 and above) will not be invited to participate in mosquito feeding assays. They will, however, be offered treatment to clear their parasitemia as described in section 7 of this protocol. The team in Kombewa will facilitate the movement of the participants from their homesteads to the KEMRI/USAMRD-A facilities where the feeding assays will take place as described in section 8.1.5.

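### The planning distribution Beta(1.5, 6) gives about 9% zero-infection feeds, not the 16% it is said to approximate, so two figures that depend on between-person spread are too favourable; the 90% power is not overturned

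*Protocol*

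**What the plan says.** All of this is in Protocol section 10.3 unless noted.

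- Earlier data from the same site: "in approximately 16% of experiments with PCR-positive gametocytes, there will be no (zero) infected mosquitoes detected", and "Greater than 50% of DSF assays have < than 5 infected mosquitoes out of 25".
- The simulation draws the number of infected mosquitoes per feed from a binomial with 25 trials and a Beta(1.5, 6) probability. The Beta is said to achieve those two features approximately, restated as "16% with 0 positive mosquitos and 50% less than 5".
- "with the current sample size of 36 subjects and 25 mosquitos per feeding assay", power to conclude equivalence at ±7 points is given as 90% when a person's probability is the same on both days, and 4% when the two days are independent draws.
- The same parameters are then carried into an illustration of power for the follow-on Phase 2b trial (Figure 13), comparing an unpaired with a before-after design over a range of efficacies. There, "correlated data has an average correlation of 0.5 and is tested with a paired t-test".
- The sample size was set mainly by logistics and budget.
- Section 8.1.4 limits who is fed upon: carriers with "very low density gametocytemia (PCR cT value of 31 and above) will not be invited to participate in mosquito feeding assays". Section 10.3 gives no cT range for the earlier data.

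**The concern.** The zero-infection share and the share below 5 together fix both the centre and the spread of a two-parameter Beta. If the zero share is wrong, the spread between people is wrong even when the centre looks right. Between-person spread largely cancels when two feeds on the same person are compared, but enters in full when the two measurements are unrelated. A Beta with too little spread therefore flatters any calculation on independent measurements: scenario 1 of the current study, and the two-group arm of the Phase 2b illustration. The study exists to inform the choice between a before-after and a two-group design, so the planning comparison should rest on a distribution that matches the data it cites.

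**Working it through.** **Inputs.** From section 10.3: 25 mosquitoes per feed, 36 pairs, Beta(1.5, 6), margin 0.07, targets 16% zeros and 50% below 5. Assumptions of mine: two one-sided tests at 0.025 each (section 10.3 gives no level; section 10.5.2 reports 95% intervals), and 20 subjects per arm or 20 pairs with 60% efficacy for the Phase 2b example, because Figure 13 is not visible.

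**1. The stated fit.** For a beta-binomial with 25 trials, P(0) = B(1.5, 31)/B(1.5, 6) = 0.0893. Summing the probabilities of 0 to 4 gives 0.5283.

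| | Target | Beta(1.5, 6) |
|---|---|---|
| No infected mosquito | 16% | 8.9% |
| Fewer than 5 | 50% (or more) | 52.8% |

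Among 36 feeds that is 36 × 0.0893 = 3.2 expected zeros, against 36 × 0.16 = 5.8.

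**2. Betas that meet both targets.** Solving for 16% zeros gives Beta(0.776, 2.708) with 52.8% below 5, and Beta(0.83, 3.16) with 55% below 5. The between-person variance is V = ab/[(a+b)²(a+b+1)]:

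- Beta(1.5, 6): 9/(56.25 × 8.5) = 0.0188
- Beta(0.776, 2.708): 0.0386
- Beta(0.83, 3.16): 0.0330

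**3. Why one power moves and the other does not.** Write μ for the mean and W = [μ(1−μ) − V]/25 for the average binomial variance of one feed. The difference between two feeds has variance 2W if p is constant and 2(V + W) if the days are independent. For Beta(1.5, 6), W = (0.16 − 0.0188)/25 = 0.00565. The SD of a difference is √(2 × 0.00565) = 0.106 for constant p and √(2 × 0.02447) = 0.221 for independent p. With 36 pairs and t = 2.03, a typical 95% half-width is 0.106/6 × 2.03 = 0.036 and 0.221/6 × 2.03 = 0.075. The second already exceeds the 0.07 margin.

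After refitting, W hardly changes, so the constant-p SD stays near 0.103 to 0.104. The independent SD rises to about 0.277 to 0.297, a half-width of about 0.094 to 0.100.

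**4. Equivalence power at ±0.07, 36 pairs (simulated, 100,000 runs).**

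| Distribution | Constant p | Independent p |
|---|---|---|
| Protocol's stated figure | 90% | 4% |
| Beta(1.5, 6), recomputed | 93.5% | 4.5% |
| Beta(0.776, 2.708) | 94.5% | 0.06% |
| Beta(0.83, 3.16) | about 95% | about 0.2% |

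The 4% is reproduced. At 0.05 per side the independent figure would be about 19%, so 0.025 per side is evidently the level used. The stated 90% is a few points below what its own inputs give; rounding or few simulation runs could explain that.

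**5. Phase 2b illustration (20 per arm or 20 pairs, 60% efficacy).** Two-group t-test power is about 88% under Beta(1.5, 6) and about 74% under either refit. Paired power is above 99% throughout. At 40% efficacy, two-group power goes from 46% to 33% and paired power stays near 90%.

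**6. The 0.5 correlation.** Two untreated feeds with constant p under Beta(1.5, 6) have correlation V/(V + W) = 0.0188/0.0245 = 0.77. If the second feed has probability 0.2p (80% efficacy), the covariance is 0.2 × 0.01882 = 0.00376. The variance after treatment is 0.04 × 0.01882 + (0.04 − 0.00235)/25 = 0.00226. The correlation is then 0.00376/√(0.02447 × 0.00226) = 0.51. At 50% efficacy it is 0.67 and at 90% it is 0.39.

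**The case against.** The strongest reply is that little turns on the error. The protocol says only that the fit is approximate, the share below 5 is right, and the number of subjects came from logistics and budget. The constant-p power does not fall when the zero share is corrected, the independent-data power was already negligible, and before-after still beats two-group in the follow-on illustration. Most of this stands. It bounds the consequence but does not rescue the sentence: 8.9% is not approximately 16%, and the same section singles out the 16% as important.

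The independent-data figure also depends on the share below 5. The bullet on earlier data says more than 50%, not exactly 50%. Beta(1, 5), with 16.7% zeros and 62.7% below 5, gives 4.9%. The fall to about 0.2% or less belongs to fits with 53 to 55% below 5.

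Three stronger readings are tempting, and the documents do not support them.

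- *That the 90% rests on the wrong distribution and fails.* It does not fail; refitting to 16% zeros leaves it at 94 to 95%.
- *That the planning data describe a population the study does not enrol.* Section 10.3 speaks of PCR-positive people without a cT limit and section 8.1.4 excludes cT 31 and above, but nothing says the earlier feeds included such carriers. If they did, removing them would plausibly lower the zero share, which pulls against the 16%. Constant-p power would drop to 88%, 83% or 76% at mean prevalences of 25%, 30% or 40%, but those means are assumed (a + b held at 7.5) and the protocol supplies none of them.
- *That the 0.5 is a mistake for 0.77.* The 0.5 is called an average and belongs to an illustration over varying efficacy. The protocol's own model yields it at about 80% efficacy, so it can be consistent with the stated parameters. What is missing is a statement that it is not the correlation of two untreated feeds.

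**Conclusion.** The statement that Beta(1.5, 6) approximately reproduces 16% zero feeds is wrong: the value is 8.9%. That result is exact and needs no assumption. A Beta meeting both targets has about twice the between-person variance.

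The consequences are limited. The 90% constant-p power holds (0.025 per side assumed). The 4% independent-data power becomes about 0.2% or less when 53 to 55% of feeds are below 5. Two-group power in the follow-on illustration is too favourable, for example 88% against 74% at an assumed 20 per arm and 60% efficacy, with paired power unchanged. The direction matters: the protocol understates, rather than overstates, the case for the before-after design, provided a person's transmission probability is constant over the 24 hours. This is worth correcting and does not threaten the study's size or its main power statement.

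**What to change.** 1. Refit the Beta to the site's earlier DSFA data. Say whether those data included carriers with cT 31 and above and, if so, restrict the fit to cT below 31. If no refit is made, replace the 16% by the 9% that the chosen Beta delivers and say that it does not match the earlier zero share.
2. Restate the 90% and 4% powers from the distribution finally used, with the level per side, and regenerate Figures 12 and 13 from it.
3. In the Phase 2b illustration, state that the 0.5 is a before/after correlation with efficacy applied, and that two untreated constant-p feeds under Beta(1.5, 6) have correlation 0.77. Do not simply substitute 0.77 for 0.5.

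The cost is a few hours of re-simulation and revised text in section 10.3. Enrolment and procedures are unaffected.
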